Wellman Labs, MGH, [name], MD	Ex vivo human torso/back skin 7.5 and 10 MHz probes	>150 exposures All shots assessed (NBTC and Eosin counter-stain)	-- Understand basic skin tissue effect (depth, dimension, control, etc.) with ultrasound -- Understand biophysical processes – selective thermal ablation and its predictability
UC San Diego, [name], MD	6 Human cadavers 7.5, 4.4 and 10 MHz probes	>1000 exposures placed in facial skin tissue At least 300 samples assessed (H&E and Trichrome-Masson staining)	-- Validate clinical treatment logistics (skin marking, lesion identification, etc.) -- Validate visual (clinical) effect of tissue shrinkage -- Verify treatment depth, control, and dose response -- Identify Trichrome-Masson stain as a potential predictor of thermal damage with UltraSite ST™ System

GUIDED THERAPY SYSTEMS, CONFIDENTIAL

Ulthera, Inc., [name], MD, PhD, [name], PhD, [name], PhD	Ex vivo porcine skin 8 in vivo porcine abdominal skin experiments 7.5, 4.4 and 10 MHz probes	>1000 exposures placed in porcine skin (in vivo and ex vivo) At least 70% of samples assessed histological (NBTC and H&E)	-- Device and application development -- Correlate experiment with numerical simulations -- Understand skin-ultrasound biophysics -- Confirm dose response
--	--	--	---

In summary, safety and efficacy for the described above studies performed with intense therapeutic ultrasound (ITU) was demonstrated.

STUDY OBJECTIVES

To evaluate the tolerance, efficacy and safety of an ultrasound therapy device to treat CET tendinosis as measured by:

- Subject survey of pain, function, and activity: Patient Rated Tennis Elbow Evaluation (PRTEE).
- Diagnostic Ultrasound Imaging, to evaluate tendon thickness, homogeneity, and gross anatomy/pathology.
- Subject self-assessment of improvement, satisfaction and treatment tolerability.
- Physician physical examination.

STUDY DESIGN

This will be a single center, controlled study involving a total of twenty-five (25) subjects with CET tendinosis (figure 2). Subjects will receive two treatments. Each treatment will be up to ten minutes (10 minutes) in duration.

[figure not shown]

Figure 1. Study Design.

STUDY OUTLINE

This study will be approximately 2 months in duration plus 2 telephone surveys at 12 and 24 weeks. Subjects who meet the criteria and provide written consent to be in the study will be included in the study.

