Subjects will receive conservative standard of care treatment plus two ITU treatments (week 0 and week 4) on the affected CET (figure 2) using the ultrasound therapy device. Treatments will be up to 10 minutes in duration. A 2, 4, and 8 week follow up period will be included to monitor the effects of the therapy post treatment. A 12 and 24-26 week telephone assessments for the primary objectives will also be included. Telephone assessments will consist of the subjects answering the survey questions over the phone.

Subject self-assessments will be conducted before the treatment phase and during the follow-up period. Physical exams will be completed by a physician. Physical therapy will be completed by a therapist. ITU treatment and diagnostic ultrasound will be performed by Guided Therapy personnel as shown in the full schedule of events (Appendix 1).

[figure not shown]

Figure 2: Treatment Area

SELECTION OF SUBJECTS**Planned number of subjects**

The study population will consist of up to 25 subjects with unilateral CET tendinosis defined as pain lasting more than 3 months with little or no improvement following conservative standard of care alone.

The selection of suitable subjects will be made according to the inclusion and exclusion criteria described in the following sections.

Inclusion Criteria

1. Subjects who are in general good health and are willing to cooperate and participate by following study requirements for the duration of the study, and to report any adverse symptoms immediately;
2. Subjects who have provided written and verbal informed consent;
3. At time of enrollment subjects are between the ages of 21 and 65 years
4. Subjects literate in English and able to complete all patient self-assessment questionnaires;

5. Subjects is willing to refrain from beginning any additional treatment during the duration of the study;
6. Subjects is willing to refrain from changing physical activity during the duration of the study;
7. Subjects diagnosed with unilateral CET tendinosis defined as pain lasting more than 3 months with little or no improvement following conservative standard of care alone.
8. Subjects with BMI ≤ 35 or at the discretion of the PI.
9. Subjects must be able to sit in a chair with their arm on an appropriate table for the treatment and diagnostic ultrasound imaging.
10. Subject must be able and willing to complete the at home therapy regimen.

Exclusion Criteria

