
If a subject meets all the inclusion/ exclusion criteria, they will be enrolled onto the study, issued a subject number and an X-ray will be scheduled.

Visit 1 and 3: (Weeks 0 and 4) Study treatments

1. Record AEs, con meds and other events
2. Administer PRTEE-A questionnaire (Appendix 2)
3. Subject self-assessment questionnaire (Appendix 3)
4. Focused Physical Evaluation
5. Diagnostic Ultrasound images taken
6. ITU treatment, and VAS assessment of treatment tolerability.
7. Physical Therapy will be performed as described (Appendix 4 – Visit 1 only)
8. Home Cold Pack & Stretching Program review and Log (Appendix 6-A and 6-B)

Visit 2, and 4: (Weeks 2 and 8) Diagnostic Ultrasound, Self-Assessments, Physical Examination

1. Record AEs, con meds and other events;
2. Administer PRTEE-A questionnaire (Appendix 2)
3. Subject self-assessment questionnaire (Appendix 3)
4. Diagnostic Ultrasound image taken;
5. Home Cold Pack & Stretching Program review and Log (Appendix 6-A and 6-B)

Phone/Online Interviews at 3 and 6 months post treatment

1. Record AEs, con meds and other events;
2. Follow-up phone interview PRTEE-A verbally administered (Appendix 2).
3. Subject self-assessment questionnaire (Appendix 3)

STUDY TREATMENT

ITU will be performed by a trained technologist, using a clinical prototype (Ulthera FDA cleared in Sept. 2009) GEN II or GEN III designed Guided Therapy Systems, LLC. Mesa, AZ USA (Appendix 7-A).

Subjects will be treated seated with their arm resting on a structure that is comfortable for the subject and technologist. Transdermal application of ITU therapy: An average energy up to 3 joules (0.5 to 3 J) will be administered to the affected CET tendon longitudinally until the maximum number of lines (12) are reached. Each line will include individual thermal zones, less than 1 mm³ in volume, centered at a depth between 2 – 6 mm, up to 2 mm apart (figure 3).

[figure not shown]
[figure not shown]

Figure 3. Zone pitch, and depth. Tendo

Treatment pattern:

Acoustic Coupling Gel will be applied every 3-5 lines.

Figure 3-1. Zone pitch, and depth.

The study treatment will be a 10 minute session using the ultrasound therapy device with coupling gel. Subjects will be treated seated with their arm resting on a structure that is comfortable for the subject and technologist.

DIAGNOSTIC ULTRASOUND IMAGING

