Diagnostic Ultrasound Imaging will be performed by a trained Sonographer using the Spark® Imaging System, manufactured by Ardent Sound, Inc., Mesa, AZ USA (Appendix 7-B)

Subjects will be imaged seated with their arm resting on a structure that is comfortable for the subject and sonographer.

PolySonic® or AquaSonic® Gel will be applied by the sonographer as required to maintain adequate acoustic coupling. (Appendix 7-C)

1

[figure not shown]
Images will be preserved with the following notations:

- Protocol ID
- Right vs. Left CET Tendon
- Treated vs. Untreated

Long Axis and Short Axis (if necessary) images will be stored at the Sonographer's discretion, to demonstrate and track the applicable anatomy/pathology in the peri-CET area.

Sonographer will also measure the thickness of the CET tendon in each applicable image.

Sonographer will scan the contralateral CET tendon in the same manner noting the change in the tendon (Right v. Left) and (Treated v. Untreated).

Common Extensor Tendon
Figure 4: representative long axis ultrasound images

Outcome measures

Subjects will complete subject reported outcome measures at 0, 2, 4, 8, 12, and 24 weeks and will undergo a focused physical examination and diagnostic ultrasound at 0, 2, 4, and 8 weeks. Adverse events will be recorded at each visit. Treatment tolerability will be assessed immediately after each treatment using the Visual Analog Scale for Pain (VAS) or Universal Pain Assessment Tool (Appendix 3-B). The VAS will be used for 2 different assessments: 1. Pain related to physical activity of the symptomatic arm before treatments and at follow-up visits and phone surveys. 2. Pain tolerance of the therapy treatment. Each of these assessments will be documented and evaluated separately.

Aim 1: reported outcomes

The principal aim of this study is to assess the efficacy of treatment and time course of response to treatment using validated subject reported outcome measures assessing pain, function and level of activity. Subjects will complete validated subject reported outcome questionnaires assessing pain, function and level of activity prior to initiating treatment and at

0, 2, 4, 8, 12, and 24 weeks after starting treatment (Appendix 2 and 3A).

Clinical Pain and Treatment Tolerance will be assessed using the Visual Analog Scale for Pain (VAS) or Universal Pain Assessment Tool (Appendix 3-B).

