Function will be assessed using three validated response forms: PRTEE - An index of the severity of CET Tendinopathy¹⁸ (Appendix 2), Self-Reported Outcome Measures (SROM)¹⁶.

Level of Activity will be assessed using the activity subscale of PRTEE¹⁸ (Appendix 2). This subscale scores quantitatively the level of difficulty subjects face when they perform basic activities of daily living. It has shown to be an accurate and reliable predictor of the activity level while performing day-to-day activities.

Statistical analysis

Data will be assessed for variance homogeneity and normality. PRTEE¹⁸, and Visual Analog Scale for Pain (VAS) or Universal Pain Assessment Tool (Appendix 3-B) scores will be assessed before and after intervention. The VAS will be used for 2 different assessments: 1. Pain related to physical activity of the symptomatic arm before and after treatment. 2. Pain tolerance of the therapy treatment. Each of these assessments will be documented and evaluated separately.

Aim 2: CET Tendon thickness

Diagnostic ultrasound imaging will be performed with an FDA approved ultrasound scanner (Spark[®] System, Ardent Sound, Inc. – Mesa, AZ, see Appendix 7-B using a coupling gel (Polysonic[®], or AquaSonic[®], Parker Laboratories, Inc., Fairfield, NJ, see Appendix 7-C) by a trained sonographer or physician. Subjects will be treated seated with their arm resting on a structure that is comfortable for the subject and technologist.

CET Tendon thickness is measured before treatment(s) and at each documented assessment (Appendix 1). Paired t tests are used to compare the CET Tendon thickness means between pre- and post-treatment between the symptomatic and treated arm and the asymptomatic and untreated arm. P<0.05 is considered to be statistically significant. Any peri-CET pathology will also be documented.

Aim 3: Assessment of safety and tolerability

Subject self-assessments of treatment tolerability will be conducted immediately after treatments, and at each follow-up visit and phone survey using a 10-point visual analog scale VAS, (Appendix 3-B). The subject will be asked to report their current level of pain and the maximum level of pain experienced since the last treatment. The surveyor will remind the subject of the VAS criteria and record their reply. The VAS is the standard for assessing pain for both clinical and research purposes²².

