Recording of adverse events will take place at all visits (see adverse event reporting form Appendix 5). Adverse events will be monitored throughout the study.

A treatment will not be administered if there is residual pain/discomfort experienced by the subject from the previous treatment.

ACCOUNTABILITY

Treatment administered to the subjects will be documented by the operator and tracked on the Case Report Form (CRF).

BREAKING THE CODE IN AN EMERGENCY

Treatment codes and allocation of treatment per subject will be accessible by the Principal Investigator of the study.

SAFETY MONITORING**ADVERSE EVENT**

An adverse event (AE) is any untoward medical occurrence in a subject, whether or not related to study product or study procedures. Adverse events include any occurrence that is new in onset, an exacerbation of a pre-existing condition and clinically significant laboratory values.

Exceptions

The following medical occurrences will not be reported as AEs;

- Pre-treatment Adverse Events; Any medical occurrence that occurs after informed consent, but before first administration of ITU treatment or first study procedure is considered as medical history and only recorded as an AE if it worsens during the study.
- Pre-existing medical condition; Events that occur with comparable frequency and severity to the subject's baseline condition are reported as medical history, not AEs unless they become exacerbated during the study.
- Pregnancy; This is not an AE however the PI must report any pregnancies to The Guided Therapy and the Institutional Review Board (IRB) for advice regarding the appropriate course of action.

Study Specific Expected Adverse Event

The following AEs are expected due to the use of these study products and/or procedures and for this specific study, they will not be regarded as AEs;

- Transient erythema may be expected as a result of the study treatment which is expected to subside after a few hours. This will not be recorded as an AE unless persistent after 24 hours.
- Subjects may experience mild-moderate tingling, warming, pain or discomfort during the study treatments. These will not be recorded as AEs unless persistent after 24 hours or if they increase to severe/unbearable sensations.

The following AEs may be expected due to the use of these study products and/or procedures and for this specific study, they will be regarded and recorded as AEs;

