TITLE: STUDY TO EVALUATE THE SAFETY, EFFICACY AND TOLERANCE OF INTENSE THERAPEUTIC ULTRASOUND (ITU) FOR THE TREATMENT OF LATERAL EPICONDYLITIS

PROTOCOL NO. and WIRB NO: 20150654

DATE: March 2, 2015

Principal Investigator: [name]

The More Foundation
[name]
[name]
[name]

Sponsor: Guided Therapy Systems
[name]
[name]

Statistical Analysis Plan:

Statistical Methods

Pain Reduction:

Pain level for subjects at the region of interest was self-reported at pre-treatment, used as baseline, and again at each follow-up at 4, 8, 12, and 26 weeks following initial treatment. The pain scale subjects used to identify their level of pain was a 10-point pain scale, where 0 = no pain, 1 = slight pain, through 10 which equates to the patients' worst imaginable pain. The goal for all subjects was to reduce pain by at least 25%. For patients reporting an initial (baseline) score ranging 6-10, this reflects a VAS pain score reduction \geq a 2 point drop; for initial scores ranging 2-5, this reflects a VAS pain score reduction \geq a 1 point drop. Pain scores reported at follow-up timepoints were compared to baseline score for each subject to determine if the goal was met by dividing the difference in the follow-up and baseline pain score by the baseline pain score. The percentage of subjects that met the pain reduction goal was calculated at each timepoint for both groups by dividing the number of subjects that achieved the pain reduction goal at that timepoint by the total number of patients that gave a pain score for that timepoint.

Patient Rated Tennis Elbow Evaluation Score Reduction:

In addition to the 10-point VAS pain scale, patients self-reported answers to questions from the Patient Rated Tennis Elbow Evaluation (PRTEE) questionnaire, which has been standardized for use in research studies to evaluate patient's level of pain and function ^[10]. Scores range from 0-100, with 0 indicating no pain and 100 indicating the worst pain imaginable in a variety of daily activities. Self-reported scores were taken at baseline and each follow-up timepoint. The average score for each timepoint were calculated, and follow-up averages were compared to baseline to calculate the percentage reduction in score.

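### As the text stands, a change from baseline in PRTEE or VAS cannot be attributed to ITU alone: study exercise starts at the same visit and no second group is defined

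*Protocol*

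**What the plan says.** **What is to be learned.** Study Objectives: "To evaluate the tolerance, efficacy and safety of an ultrasound therapy device to treat CET tendinosis as measured by" PRTEE, imaging, self-assessment and physical examination. The purpose statement in the Introduction likewise names the ITU device. Aim 1 adds: "The principal aim of this study is to assess the efficacy of treatment and time course of response to treatment".

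**What subjects receive.** Study Outline: "Subjects will receive conservative standard of care treatment plus two ITU treatments (week 0 and week 4) on the affected CET". No other regimen is described. The procedure list for Visits 1 and 3 states: "Physical Therapy will be performed as described (Appendix 4 – Visit 1 only". The same list, and the calendar in Appendix 1, first show the home programme review at Visit 1, the visit of the first ITU. Inclusion criterion 10 makes willingness to complete the home regimen a condition of entry. The exercise leaflet reproduced in Appendices 4 and 6-A says that the exercises alone can be expected, in most cases, to ease the pain after some 4 to 6 weeks.

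**How PRTEE and VAS are analysed.** The statistical paragraph under Aim 1 looks at scores before and after intervention. The SAP compares each subject's pain score, and the average PRTEE score, with baseline. Only tendon thickness has an internal comparator, the untreated arm. Aim 2: "Paired t tests are used to compare the CET Tendon thickness means between pre- and post-treatment between the symptomatic and treated arm" and the asymptomatic, untreated arm.

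**Traces of a second group.** Study Design: "This will be a single center, controlled study involving a total of twenty-five (25) subjects with CET tendinosis". Breaking the Code in an Emergency: "Treatment codes and allocation of treatment per subject will be accessible by the Principal Investigator of the study". Data Handling speaks of subjects being *randomised*. SAP, Pain Reduction: "The percentage of subjects that met the pain reduction goal was calculated at each timepoint for both groups". Neither document says what a second group would receive.

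**The concern.** The question is about one component, the device. What the text describes is a package whose parts start together. A before-after change then reflects ITU, the study's exercise programme, natural recovery, regression to the mean and placebo response in unknown proportions. Subjects know that they are treated, and both outcomes are self-reported.

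The exercise component cannot be set aside as inert, because the protocol's own appendices expect it to relieve pain inside the follow-up window.

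At stake is what the trial may conclude. If no second group exists, the responder percentages and mean PRTEE reductions in the SAP have nothing to be read against, and no observed value would show that the device did the work. A larger single-group sample would estimate the same mixture more precisely.

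**Working it through.** **1. The plan's own figure.** Statistical Methods gives 25 per-protocol subjects, two-sided alpha 0.05 and 80% power, with no effect size, SD, test or endpoint, so it cannot be reproduced. If it refers to a one-sample or paired comparison, the implied detectable change is (1.960 + 0.842)/√25 = 0.56 SD of change (0.58 with the t distribution). That concerns detecting a change, not attributing it, so the point does not rest on it.

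**2. Can the schedule separate ITU from exercise?** Both start at week 0. The week 0 questionnaire is taken before the first treatment.

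| Outcome | Reading weeks | Before both start | After both start | After one, before the other |
|---|---|---|---|---|
| PRTEE (protocol) | 0, 2, 4, 8, 12, 24 | 1 | 5 | 0 |
| Pain (SAP) | 0, 4, 8, 12, 26 | 1 | 4 | 0 |

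The second ITU, at week 4, comes without a PT session, but the home programme continues, so later readings still mix the two. The count covers the study's own schedule. Exercise done before entry is a separate matter, taken up under the objection.

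The leaflet's 4 to 6 weeks, counted from Visit 1, end before the week 8, 12 and 24–26 readings.

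**3. Is there another comparator for PRTEE or VAS?**

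- *Own baseline*: yes, but it carries every non-ITU influence listed above.
- *Contralateral arm*: used for tendon thickness only. It is asymptomatic, and PRTEE asks about the affected arm.
- *Literature*: Statistical Methods mentions a descriptive comparison with published values, but gives no value or source.
- *Second group*: implied by *controlled*, *allocation*, *randomised* and *both groups*, never defined. The Study Design figure is not shown.

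**4. Illustration only: the SAP pain goal with zero ITU effect.** All inputs in this step are assumed. Take whole-number scores and baseline 6 to 8, where the SAP's 2-point rule and its 25% rule agree (25% of 6, 7 and 8 is 1.5, 1.75 and 2, so each needs a 2-point fall). Let the change be normal with mean fall d from causes other than ITU, and SD s. A fall of at least 2 whole points corresponds to at least 1.5 before rounding:

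P(goal met) = 1 − Φ((1.5 − d)/s)

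Example: d = 1, s = 2.0 gives 1 − Φ(0.25) = 40.1%, or 10 of 25.

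| Mean fall d | s = 1.5 | s = 2.0 | s = 2.5 | Of 25 subjects |
|---|---|---|---|---|
| 0 | 15.9% | 22.7% | 27.4% | about 4–7 |
| 1 | 36.9% | 40.1% | 42.1% | about 9–11 |
| 2 | 63.1% | 59.9% | 57.9% | about 14–16 |

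The documents give no figure for choosing among these rows. The table shows only that the goal can be met by a sizeable share of subjects without any device effect.

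**The case against.** **A control group may exist.** The design figure is not available to us, four separate terms point to more than one group, and the SAP would then have a reference percentage after all. This stands as a limit. A reader might infer that the trial certainly has no control group, or that the SAP certainly has no reference value. The documents do not support either. What they support is that a second group is named and never defined, while the text that describes treatment gives ITU without exception.

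**Entry rules already screen out easy responders.** Inclusion 7 requires over 3 months of pain that had barely improved on conservative care. Exclusion 3 permits standard of care up to entry, and inclusions 5 and 6 bar new treatments and changes in physical activity. This stands in part: it makes a large exercise effect, or early spontaneous recovery, less likely, and some subjects may already have been exercising. But prior care is not specified (the Introduction says only that it may include stretching and strengthening), and nothing requires that subjects had already done a comparable programme. Appendix 4 is still to be settled with the site and Appendix 6-A is an example, so the programme itself is not fixed. Later recovery, regression to the mean and placebo response remain possible.

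**The package is disclosed and no ITU-only claim is made.** True of the Study Outline and of the SAP. But the objective, which a report will answer, names the device alone.

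**A single group is acceptable in a small early study.** Agreed. The point asks that the claim fit the design, not that an arm be added.

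**Conclusion.** The point holds and should be fixed. As the text stands, PRTEE and VAS changes belong to ITU together with PT, home exercise and the passage of time, and cannot be assigned to ITU alone. On the study's schedule, none of the 5 post-baseline PRTEE readings or 4 post-baseline SAP pain readings separates the components, and no other comparator for these outcomes is specified.

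This rests on the written text. A control group defined in the missing figure would change the remedy, but would still leave the wording to be completed.

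Two stronger readings go too far. A reader might infer that ITU does not work, or that exercise explains any improvement. The documents show neither, only that the two cannot be told apart. A reader might also take the 16–63% span in the illustration as the expected background response. It follows entirely from assumed baseline, mean fall and SD, and has no source in the documents.

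**What to change.** **If there is no concurrent control group:** delete *controlled* (Study Design), *allocation* (Breaking the Code in an Emergency), *randomised* (Data Handling) and *both groups* (SAP, Pain Reduction). In Study Objectives, Aim 1 and the SAP, state that the PRTEE and VAS results are uncontrolled changes from baseline under ITU given with PT and home exercise, and that no ITU-only efficacy claim will be made.

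**If there is a control group:** state what it receives, in particular whether it has the same PT and home programme, and make the between-group comparison the basis of any ITU claim.

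The first route costs wording in two documents and a more modest claim, with no added subjects or visits. The second costs precision if the total stays at 25. With an assumed 13/12 split, the difference detectable with 80% power at two-sided 0.05 is (1.960 + 0.842) × √(1/13 + 1/12) = 1.12 SD of change, or 1.17 SD with the t distribution.

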Subjects may discontinue from the clinical study at any time. In addition, the Principal Investigator (PI) or designee has the right to withdraw a subject for any reason that is in the best interests of the subject. The subject must inform the Investigator immediately if they intend to withdraw. Subjects may be asked to come to the study facility to complete some end of study procedures.

The Investigator can remove the subject from this study without their consent for any reason, including, but not limited to:

- His/her judgment that any condition or circumstance may jeopardize their welfare or the integrity of the study.
- Their failure to follow the instructions of the investigator(s) (protocol non-compliance)
- Subject BMI exceeds ≥ 35 during the courses of the study.
- If the study is stopped by GTS and/or Principal Investigator of the study prior to completion.

CLINICAL ASSESSMENTS

Assessment of Efficacy

Primary:

The primary endpoint(s) for efficacy and tolerability will be the total score of the PRTEE questionnaire (Appendix 2), subject self-assessment of improvement and satisfaction (SROM-Appendix 3-B), and Visual Analog Scale for Pain (VAS) or Universal Pain Assessment Tool (Appendix 3-C).

Secondary:

The secondary endpoint for efficacy will be a measured reduction in tendon thickness by diagnostic ultrasound, and a physical examination.

PRTEE Questionnaire

The PRTEE questionnaire (**Appendix 2**) evaluates three domains clinically relevant to patients (pain, function, and activity) and was specifically developed to assess the clinical severity of CET tendinopathy. It is composed of 15 questions that cover 3 domains of pain (questions 1 through 5), function for specific activities (questions 6 through 11), and general activities (questions 12 through 15). All questions are scored 0 – 10. Higher scores indicate more severe CET tendinopathy. The PRTEE questionnaire has been validated and shows good test-retest reliability¹⁸

Physical Examination

Medical History: Review patient's medical history questionnaire. Review any diagnostic imaging, tests, or work up listed under longitudinal medical record and centrality. Ask about possible trauma or history of injuries to the symptomatic arm. Review athletic history (tennis, golf, etc) and subject's pre-study exercise regimen (if any). Height, Weight (BMI) will also be documented.

History of Present Illness: Most common complaint is of elbow pain.

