Additionally SAEs must be reported immediately to the IRB Title with 24 hours of the site staff becoming aware of the event. The contact details for reporting any expedited AE are given in the Contacts section of this protocol.

In the event that the percent of study related AEs is $\geq 25\%$ for a specific AE symptom, the IRB Title should be notified within 24 hours.

FOLLOW-UP OF ADVERSE EVENTS

If an AE is ongoing at the end of the study, follow-up will be performed until the AE has resolved. Follow-up may take the form of subject visits, a referral to another specialist, site telephone calls to the subject or letters from the treating physician.

The PI or designee must comply with the specific reporting requirement(s) of the ethics committee.

PREGNANCY

Females may not participate in this study if they are pregnant, breastfeeding, were pregnant or gave birth within the last three months or are planning a pregnancy during the course of the study.

GUIDED THERAPY SYSTEMS, CONFIDENTIAL

If the subject thinks they have become pregnant during the study it is important that they inform the study doctor immediately. If the subject becomes pregnant or thinks that they may be pregnant, they will be removed from the study.

STATISTICAL CONSIDERATIONS

SAMPLE SIZE CALCULATION

Up to 25 subjects will be enrolled onto the study to ensure a minimum of 25 subjects complete.

STATISTICAL METHODS

A sample size of 25 per protocol subjects will be required to demonstrate statistical significance (two-sided alpha=0.05; 80% power). Descriptive statistics will be calculated for comparison to the values noted in the existing literature.

MONITORING

The PI agrees that the site will permit, if required, study-related monitoring, audits, IRB/IEC review, and regulatory inspection(s), providing direct access to source data/documents.

Sponsor personnel, or their designees, may monitor the study. The monitor has the responsibility to familiarise the PI and the entire centre staff involved in the study with Therapy procedures. The monitor can visit the clinical study centre on a regular basis such as before the first subject has been enrolled, during the course of the study, and at study completion. The monitor must maintain the confidentiality of the study documents. Regular visits may be made to monitor clinical procedures throughout the study duration.

DATA HANDLING AND RECORD KEEPING

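### The two-sided alpha of 0.05 and 80% power claimed for 25 subjects belong to no identifiable test: three unranked primary endpoints, five follow-up times, and no test, effect size or success rule.

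*Protocol*

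**What the plan says.** Under Assessment of Efficacy the Protocol states: "The primary endpoint(s) for efficacy and tolerability will be the total score of the PRTEE questionnaire (Appendix 2), subject self-assessment of improvement and satisfaction" (the SROM form), "and Visual Analog Scale for Pain (VAS) or Universal Pain Assessment Tool (Appendix 3-C"). No ranking is given, and no rule says whether one or all of the three must succeed.

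Under Outcome measures: "Subjects will complete subject reported outcome measures at 0, 2, 4, 8, 12, and 24 weeks". That is baseline plus five follow-ups, and Appendix 1 agrees. No visit is named as decisive. The Study Outline describes the 12 and 24-26 week calls as serving the primary objectives, so week 8 cannot be inferred by default. The same section adds "The VAS will be used for 2 different assessments": activity pain and tolerance of the treatment.

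Under Statistical Methods: "A sample size of 25 per protocol subjects will be required to demonstrate statistical significance", with "two-sided alpha=0.05; 80% power". The next sentence promises only descriptive statistics to set beside the literature.

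The SAP summarises two outcomes: the percentage of subjects who reach a 25% pain reduction, and the percentage reduction in mean PRTEE. Pain is taken at baseline and "again at each follow-up at 4, 8, 12, and 26 weeks following initial treatment". The SAP contains no hypothesis test, alpha, primary time point or multiplicity rule, and it does not cover SROM.

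The only test named in either document is the paired t test on tendon thickness (Protocol, Aim 2, P<0.05). Tendon thickness is a secondary endpoint, and the power statement does not refer to it.

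**The concern.** An alpha and a power describe one decision rule: a named outcome at a named time, a test, and the effect it is meant to detect. Here the figures are given without the rule. With three instruments and five follow-ups, the rule could be completed in many ways after the data are seen, and the sponsor performs the analysis. The trial could not then be judged against its own claim. Nobody could say whether a favourable result was the one that 25 subjects were planned to show, or one of several candidates.

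**Working it through.** **Inputs from the documents.** n = 25, two-sided alpha 0.05, power 80% (Protocol, Statistical Methods); 3 primary endpoints (Assessment of Efficacy); 5 follow-ups (Outcome measures, Appendix 1); 2 outcomes and 4 pain follow-ups (SAP).

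**Not in the documents, so assumed.** The test (a paired t test on change from week 0), the effect d in SD units of that change, and the correlations between tests. Rates at non-zero correlation were simulated with n = 25.

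**Step 1: try to reproduce 25.** It cannot be derived forwards, because no effect, SD or reference rate is given. Working backwards from n = 25, 80% power and two-sided 0.05 (unless noted):

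- Paired or one-sample, normal approximation: d = (1.960 + 0.842)/√25 = 0.560. With the noncentral t: d = 0.584.
- The same test one-sided: d = 0.512.
- Two groups of 12 and 13: d = 2.802 × √(1/12 + 1/13) = 1.12.
- Single-arm responder test (exact binomial, upper tail at most 0.025): 46% against an assumed reference rate of 20%, or 77% against 50%.

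For a paired t test the required n is 90 at d = 0.3, 34 at d = 0.5 and 15 at d = 0.8. The number 25 fits many tests and identifies none.

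**Step 2: if any one endpoint may win, each tested at 0.05.** For k independent tests the family-wise error is 1 − 0.95^k.

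| Tests | Independent | Correlated |
|---|---|---|
| 3 endpoints, one visit | 1 − 0.95³ = 14.3% | about 13.5% at correlation 0.3; about 10% at 0.8 |
| 3 endpoints × 5 visits | 1 − 0.95¹⁵ = 53.7% | about 37% when all pairs correlate at 0.5; about 21% at 0.8 |
| SAP: 2 outcomes × 4 visits | 1 − 0.95⁸ = 33.7% | about 27% at 0.5; about 18% at 0.8 |

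In the SAP row, the correlation between two tests that differ in both outcome and visit is the product of the two correlations.

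**Step 3: if the three endpoints are adjusted by Bonferroni at one visit.** Alpha per test is 0.05/3 = 0.0167. At d = 0.584, power for each endpoint falls from 80% to 63.7%. The change detectable with 80% power rises to 0.689 SD.

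**Step 4: if all three must win at one visit.** Alpha does not inflate. With 80% power on each endpoint, joint power is 0.8³ = 51% if independent, about 61% at correlation 0.5 and about 72% at 0.9.

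**Step 5: completers.** The Protocol enrols up to 25 in order to have at least 25 complete, so the 0.584 SD figure holds only with no dropout.

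**The case against.** The strongest reply is that there is no multiplicity to control. No hypothesis test is planned for any primary endpoint, the SAP is purely descriptive, and the repeated visits serve a stated aim of describing the time course of response. On this view the defect is only an unsupported sample-size sentence.

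Much of that stands. A reader might infer that a significant result on any endpoint at any visit may be reported as success, and that the plan's error rate is therefore 24% to 42%, or even 54%. The documents do not support this:

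- No any-endpoint rule is written. If all endpoints were meant to succeed, alpha would not inflate at all.
- The 15 tests are a construction. SROM consists of six ordinal items, mostly asking about change since the start, with no defined total and no meaningful baseline to pair. A paired t test does not fit it.
- The SAP has two outcomes and four pain visits, not three and five.
- The 24% to 42% range requires endpoint and visit correlations of 0.8 to 0.5 to be multiplied, so that at 0.5 many pairs correlate at only 0.25. With all pairs at 0.8 to 0.5 the range is 21% to 37%.

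The reply does not rescue the power statement. A descriptive study has no use for a claim of significance with 80% power, and a confirmatory one needs a named test. The text has to change in either case.

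**Conclusion.** The concern holds in this form: the stated alpha and power are attached to no endpoint, visit, test or effect, and the SAP does not supply them.

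The pair of figures fits neither natural reading. If any endpoint can win without adjustment, the 5% fails: about 10% to 14% for three tests at one visit, and more if visits are also counted. If all must win, the 80% fails whenever each endpoint has just 80% power: about 51% to 72% jointly. That shortfall would shrink if the true effects were larger than 0.584 SD.

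These sizes rest on assumed paired t tests, assumed correlations and 25 completers. They show what the gap could cost and are not the plan's own error rate, which cannot be computed. The finding that no test can be identified rests on the text alone.

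**What to change.** 1. In the Protocol's Assessment of Efficacy and in the SAP, name one primary endpoint: within-subject change in PRTEE total from week 0. The Protocol describes this instrument as validated and specific to the condition.
2. Name one visit before any data are seen. Week 8 is the last clinic visit, but the sponsor must reconcile that choice with the Study Outline, which ties the 12 and 24-26 week calls to the primary objectives, and with the SAP's week 26.
3. Specify one paired t test at two-sided 0.05.
4. Make VAS pain, SROM (summarised as ordinal responses) and all other visits secondary, with confidence intervals where applicable. Use Holm if significance will be claimed on any of them.
5. Restate the power line: 25 completers give 80% power for a mean change of 0.58 SD in PRTEE total at that visit. Say that enrolling up to 25 leaves no allowance for dropout. The 0.58 SD is solved back from n = 25, so the sponsor should add why a change of that size is worth detecting.

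If the study is meant to be descriptive, as the SAP implies, delete the power and significance claim instead and report estimates with confidence intervals.

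Either route costs a few lines of wording and needs no extra subjects or visits. Under the first, VAS and SROM lose primary status.
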